12.7 Adverse Events of Special Interest (AESI) for Atezolizumab

Adverse events of special interest (AESI) are required to be reported by the investigator to the sponsor immediately (i.e., no more than 24 hours after learning of the event). AEs of special interest are as follows:

- Cases of potential drug-induced liver injury that include an elevated ALT or AST in combination with either an elevated bilirubin or clinical jaundice, as defined by Hy's Law (see [Section 5.5.1.2 Potential Cases of Drug-Induced Liver Injury](#))
- Suspected transmission of an infectious agent by the study treatment, as defined below:
 - Any organism, virus, or infectious particle (e.g., prion protein transmitting transmissible spongiform encephalopathy), pathogenic or non-pathogenic, is considered an infectious agent. A transmission of an infectious agent may be suspected from clinical symptoms or laboratory findings that indicate an infection in a subject exposed to a medicinal product. This term applies only when a contamination of study treatment is suspected.
- Pneumonitis
- Colitis
- Pneumonitis
- Colitis
- Endocrinopathies: diabetes mellitus, pancreatitis, adrenal insufficiency, hyperthyroidism, and hypophysitis
- Hepatitis, including AST or ALT > 10 × ULN
- Systemic lupus erythematosus
- Neurological disorders: Guillain-Barré syndrome, myasthenic syndrome or myasthenia gravis, and meningoencephalitis
- Events suggestive of hypersensitivity, infusion-related reactions, cytokine-release syndrome, influenza-like illness, systemic inflammatory response syndrome, and systemic immune activation
- Nephritis
- Ocular toxicities (e.g., uveitis, retinitis, optic neuritis)
- Myositis
- Myopathies, including rhabdomyolysis
- Grade ≥ 2 cardiac disorders (e.g., atrial fibrillation, myocarditis, pericarditis)
- Vasculitis
- Autoimmune hemolytic anemia
- Severe cutaneous reactions are a known risk (e.g., Stevens-Johnson syndrome, dermatitis bullous, toxic epidermal necrolysis)

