3.2.2.2 Atezolizumab Dose Interruption

Refer to the following for atezolizumab dose modification recommendations:

Table 4 Recommended Dosage Modifications for Adverse Reactions (Atezolizumab)

Adverse Reaction	Severity of Adverse Reaction ^a	Dosage Modifications
Pneumonitis [see Warnings and Precautions (5.1) in the package insert]	Grade 2	Withhold dose until Grade 1 or resolved and corticosteroid dose is less than or equal to prednisone 10 mg per day (or equivalent)
	Grade 3 or 4	Permanently discontinue
Hepatitis [see Warnings and Precautions (5.2) in the package insert]	AST or ALT > 3 and ≤ 8 x ULN or total bilirubin > 1.5 and ≤ 3 x ULN	Withhold dose until Grade 1 or resolved and corticosteroid dose is less than or equal to prednisone 10 mg per day (or equivalent)
	AST or ALT > 8 x ULN or total bilirubin > 3 x ULN	Permanently discontinue
Colitis or diarrhea [see Warnings and Precautions (5.3) in the package insert]	Grade 2 or 3	Withhold dose until Grade 1 or resolved and corticosteroid dose is less than or equal to prednisone 10 mg per day (or equivalent)
	Grade 4	Permanently discontinue
Endocrinopathies (including but not limited to hypophysitis, adrenal insufficiency, hyperthyroidism, and type 1 diabetes mellitus) [see Warnings and Precautions (5.4) in the package insert]	Grade 2, 3, or 4	Withhold dose until Grade 1 or resolved and clinically stable on hormone replacement therapy.
Other immune-mediated adverse reactions involving a major organ [see Warnings and Precautions (5.5) in the package insert]	Grade 3	Withhold dose until Grade 1 or resolved and corticosteroid dose is less than or equal to prednisone 10 mg per day (or equivalent)
	Grade 4	Permanently discontinue
Infections [see Warnings and Precautions (5.6) in the package insert]	Grade 3 or 4	Withhold dose until Grade 1 or resolved
Infusion-Related Reactions [see Warnings and Precautions (5.7) in the package insert]	Grade 1 or 2	Interrupt or slow the rate of infusion
	Grade 3 or 4	Permanently discontinue
Persistent Grade 2 or 3 adverse reaction (excluding endocrinopathies)	Grade 2 or 3 adverse reaction that does not recover to Grade 0 or 1 within 12 weeks after last TECENTRIQ dose	Permanently discontinue
Table continued on next page		

Adverse Reaction	Severity of Adverse Reaction ^a	Dosage Modifications

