7 STATISTICAL METHODOLOGY

7.1 General Considerations

For continuous variables, descriptive statistics will include the number of subjects (n), mean, standard deviation, median, minimum and maximum. When needed, the use of other percentiles (e.g., 10%, 25%, 75% and 90%) will be mentioned in the relevant section. In addition, for continuous PK parameters, the coefficient of variation will be calculated and for C_{max} and AUC the geometric mean will also be calculated. Frequencies and percentages will be displayed for categorical data. Percentages by categories will be based on the number of subjects with no missing data, i.e. will add up to 100%. Kaplan-Meier survival curves will be displayed for time-to-event variables and median survival time will be estimated with 2-sided 95% confidence interval (CI).

Safety analysis and other summaries based on SAF will be presented by actual treatment received. Pharmacokinetic summaries based on will be presented by actual treatment received. For subjects with dose change, actual treatment refers to the first dose received before dose change.

All data processing, summarization, and analyses will be performed using SAS[®] Version 9.3 or higher on Unix. Specifications for table, figure, and data listing formats can be found in the TLF specifications for this study.

Baseline is defined as the last available measurement prior to the first dose of study drug. Unless otherwise specified, all summaries and analysis will be presented by phase.

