7.5.1 Adverse Events

Any adverse event (AE) recorded on treatment including within 30 days from the last study treatment will be classified as treatment-emergent AE (TEAE) and will be summarized.

Summaries and listings of TEAEs and Serious TEAEs include SAEs upgraded by the Sponsor based on review of the Sponsor's list of Always Serious terms if any upgrade was done.

The number and percent of subjects experiencing one or more AE(s) will be summarized by SOC and PT using MedDRA and will be graded according to the National Cancer Institute Common Terminology Criteria for Adverse Events (NCI-CTCAE) version 5.0. The number and percentage of subjects with at least one grade 3 or higher AE will also be summarized by SOC and PT.

An overview table will include the following details:

- Number and percentage of subjects with TEAEs,
- Number and percentage of subjects with causally drug related TEAEs,
- Number and percentage of subjects with serious TEAEs and Astellas upgraded serious TEAE,
- Number and percentage of subjects with serious drug related TEAEs and Astellas upgraded serious drug related TEAE,
- Number and percentage of subjects with TEAEs leading to permanent discontinuation of study drug,
- Number and percentage of subjects with drug related TEAEs leading to permanent discontinuation of study drug,

- Number of deaths, and
- Number and percentage of subjects with grade 3 or higher TEAEs.

The number and percentage of subjects with TEAEs, as classified by SOC and PT will be summarized by period, cohort and dose level. Summaries will be provided for:

- TEAEs
- Drug related TEAEs,
- Serious TEAEs and Astellas upgraded serious TEAE,
- Drug related serious TEAEs and drug related Astellas upgraded serious TEAE,
- TEAEs leading to permanent discontinuation of study drug,
- Drug related TEAEs leading to permanent discontinuation of study drug,
- TEAEs excluding serious adverse events that equal to or exceed a threshold of 5% in any dose level,
- Common TEAEs that equal to or exceed a threshold of 5% in any dose level, and
- Grade 3 or higher TEAEs.

The number and percentage of subjects with TEAEs, as classified by PT only, will be summarized.

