AE summary tables will include subject counts as opposed to AE counts. If a subject experiences more than one episode of a particular AE, the subject will be counted only once for that AE. If a subject has more than one AE that code to the same preferred term, the subject will be counted only once for that preferred term. Similarly, if a subject has more than one AE within a SOC, the subject will be counted only once in that SOC.

The number and percentage of subjects with TEAEs, as classified by SOC and PT will also be summarized by NCI-CTCAE severity grade and by relationship to study drug. In the subject count, if a subject has multiple TEAEs with the same SOC or PT, but with differing severity grade or relationship, then the subject will be counted only once with the worst severity grade and highest degree of relationship, however, if any of the severity grade or relationship values are missing then the subject will be counted only once with missing severity grade or relationship. Drug related TEAEs will be presented in a similar way by severity grade only.

The number and percentage of subjects with adverse events of special safety interest (AESIs) for Atezolizumab will be summarized by PT. See [Appendix 12.7 Adverse Events of Special Interest (AESI) for Atezolizumab] for further details.

All summaries of AEs will include only TEAEs unless otherwise stated. All AEs, deaths, SAEs and withdrawals due to adverse events will be displayed in listings.

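### SAP 7.5.1 tabulates atezolizumab AESIs by preferred term, so the table as described gives no subject count or worst grade for the multi-condition groups in protocol Appendix 12.7 (minor, cheap to improve)

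*SAP*

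**What the plan says.** SAP 7.5.1 has one sentence on summarizing atezolizumab AESIs, followed by a pointer to Appendix 12.7: "The number and percentage of subjects with adverse events of special safety interest (AESIs) for Atezolizumab will be summarized by PT". No other AESI summary is described in the SAP.

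Protocol Appendix 12.7 mixes single conditions, such as pneumonitis, colitis and nephritis, with groups. Two examples of groups are "Endocrinopathies: diabetes mellitus, pancreatitis, adrenal insufficiency, hyperthyroidism, and hypophysitis" and "Events suggestive of hypersensitivity, infusion-related reactions, cytokine-release syndrome, influenza-like illness, systemic inflammatory response syndrome, and systemic immune activation". The cardiac entry admits only events of grade 2 or higher and gives its conditions as examples.

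The counting rules in SAP 7.5.1 work at the level of the single AE, the PT and the SOC. At the highest level, "if a subject has more than one AE within a SOC, the subject will be counted only once in that SOC". The worst-grade rule applies to the TEAE tables by SOC and PT. A general table by PT is also planned: "The number and percentage of subjects with TEAEs, as classified by PT only, will be summarized".

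SAP 7.1 leaves layouts to another document: "Specifications for table, figure, and data listing formats can be found in the TLF specifications for this study". SAP 6.2.4 says that AESIs are defined in the Safety Review Plan for ASP2215. Neither of those documents is available here.

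**The concern.** For a grouped immune-mediated toxicity, the useful figures are how many subjects had any event in the group and how severe their worst event was. PT rows do not add up to the first figure, because one subject can contribute to several rows. They do not give the second, because the AESI sentence mentions no grade. A PT table of AESIs also selects rows from the PT-only TEAE table that is already planned, without adding a grouped count.

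Safety and tolerability is a primary endpoint, and atezolizumab is the drug being added to gilteritinib. What is at stake is how easily the AESI table can be read; no inference depends on it.

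**Working it through.** The plan states no figure on this point, so there is none to reproduce. The check compares the texts and then sizes the gap with assumed counts.

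**Step 1: how far Appendix 12.7 is grouped.** Counting pneumonitis and colitis once each (both are printed twice), there are 17 distinct entries. Those naming three or more conditions are:

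- endocrinopathies: 5
- neurological disorders: 3 (myasthenic syndrome or myasthenia gravis taken as one)
- the hypersensitivity, infusion-reaction and cytokine-release group: 6
- ocular toxicities: 3
- cardiac disorders of grade 2 or higher: 3
- severe cutaneous reactions: 3

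That is six entries and 5 + 3 + 6 + 3 + 3 + 3 = 23 named conditions. The other 17 − 6 = 11 entries do not group three or more conditions. For single-condition entries, a PT row may come close to the category.

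**Step 2: whether another rule supplies the group count.** The once-per-subject rules in SAP 7.5.1 cover AE, PT and SOC. An Appendix 12.7 group is none of these, and the SAP does not equate one with a SOC. SAP 6.2.4, 7.1, 7.5.2.1, 7.8 and 7.9 contain no category-level AESI row, and the overview table in 7.5.1 has no AESI line.

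**Step 3: what PT rows reveal about a group.** If the PTs in a group have subject counts a1, ..., ak, the number of subjects with any event in the group lies between max(ai) and the smaller of the sum of the ai and n. The rows alone do not say where.

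**Step 4: size.** SAP 7.1 says: "Unless otherwise specified, all summaries and analysis will be presented by phase". The denominator is therefore taken as the full phase 2 size, n = 49. The documents give no AESI rates, so the counts are assumed. The Clopper-Pearson 95% limits for x of n are the 0.025 quantile of Beta(x, n − x + 1) and the 0.975 quantile of Beta(x + 1, n − x).

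| Assumed PT rows | Lower bound | Upper bound |
|---|---|---|
| 5, 0, 0 | 5/49 = 10.2% (3.4 to 22.2) | 5/49, the same |
| 5, 1, 0 | 5/49 = 10.2% (3.4 to 22.2) | 6/49 = 12.2% (4.6 to 24.8) |

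The difference in the second row is one subject, 1/49 = 2.0 percentage points. If phase 2 stopped after stage 1, one subject would be 1/22 = 4.5 percentage points. In both cases this is small beside the width of the interval.

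**Step 5: whether a plain category table would work as it stands.** Some Appendix 12.7 entries overlap: liver injury meeting Hy's law with hepatitis, and myositis with myopathies. A table with one row per entry could show the same subject in two rows, so the remedy has to deal with this.

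**The case against.** The strongest reply is that this is a preference about table layout. Nothing in the documents requires AESIs to be summarized by category, and Appendix 12.7 serves immediate reporting to the sponsor, not analysis. Reporting by PT with all AEs listed is a usable descriptive specification. With at most 49 phase 2 subjects, an exact tally from the listings is easy, and tables by SOC, PT and grade are planned as well. Safety decisions rest on DLTs, not AESIs. The AESI sentence could even be read as already promising an overall count of subjects with an AESI. Row structures and term lists could also sit in the TLF specifications or the Safety Review Plan.

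Most of this stands, and it is why the point is minor. The information is not lost. What remains is that the planned AESI table does not itself show the grouped count or worst grade, and that supplying them costs little.

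SAP Table 4 lends only weak support. Its row "Endocrinopathies (including but not limited to hypophysitis, adrenal insufficiency, hyperthyroidism, and type 1 diabetes mellitus") governs dose modification, and its membership differs from Appendix 12.7, which also names pancreatitis and does not restrict the type of diabetes. It shows that a similar heading is in use, not that it is a unit for counting.

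Two stronger readings are tempting, and the documents do not support either:

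- A reader might infer that terms could be assigned to groups after the data are seen. That cannot be established without the TLF specifications and the Safety Review Plan. A PT table forms no groups, and the summary involves no test or comparison.
- A reader might infer a five-fold uncertainty: five endocrinopathy rows of 1/49 give bounds of 1/49 (2.0%) and 5/49 (10.2%). The lower bound requires one subject to have all five endocrinopathies, so this is an extreme case and not a fair measure of the gap.

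**Conclusion.** The point holds as a minor, inexpensive improvement to a descriptive safety table. As described in the SAP, the AESI table gives neither the number of subjects with any event in a multi-condition group nor their worst grade; six Appendix 12.7 entries are affected. A realistic discrepancy is of the order of 5/49 against 6/49, on assumed counts, and it vanishes when only one PT in a group occurs. The CRc test, the sample size, dose escalation and the DLT pause rule are untouched.

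The conclusion concerns the SAP text only. It would reduce to a missing cross-reference if the TLF specifications or the Safety Review Plan already define category rows.

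**What to change.** In SAP 7.5.1, replace the PT-only AESI summary with one by medical category based on Appendix 12.7:

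- Nest the PTs under each category.
- Count each subject once per category at worst grade, for any grade and for grade 3 or higher.
- Add an any-AESI row.
- Fix the PT-to-category list before database lock.
- Apply the grade 2 threshold to the cardiac category.
- Merge the overlapping entries (Hy's law liver injury with hepatitis; myositis with myopathies), or footnote that a subject may appear in more than one category.

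If the TLF specifications or the Safety Review Plan already contain this, cite them in 7.5.1 instead. SAP 6.2.4 should also state that atezolizumab AESIs follow protocol Appendix 12.7, because it currently names only the ASP2215 plan.

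The cost is a change of SAP wording, one mapping list and a longer table shell. No new data are needed: protocol 5.5.8 already has AESIs reported on the SAE/Special Situation worksheet, and all AEs are graded.

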7.5.2 Clinical Laboratory Evaluation

The baseline visit is the last measurement taken prior to initial study drug administration.

Quantitative clinical laboratory variables, i.e., hematology, serum chemistry, coagulation and urinalysis will be summarized using mean, standard deviation, minimum, maximum and median at each visit. Additionally, change from baseline will be calculated as the

post-baseline value minus the baseline value and summarized in the same way. Each laboratory result will be classified as low (L), normal (N), or high (H) at each visit according to the laboratory supplied reference ranges.

The number and percentage of subjects below and above reference range will be summarized at each visit.

Frequency tabulations of qualitative clinical laboratory variables (urinalysis) will be presented at each visit.

Clinically significant abnormalities in laboratory values will be presented.

For hematology and chemistry two types of shift tables will be presented:

- Shift tables of changes based on reference range defined category (low, normal, high) from baseline to each visit as well as worst finding during the treatment period, and
- Summary shifts of changes based on reference range defined category from baseline to each visit as well as worst finding during the treatment period (shift from high or normal to low, shift from low or normal to high, categorized increase [shift from low to normal or from normal to high], categorized no change [value stays in the same reference range], categorized decrease [shift from high to normal or from normal to low]).

Laboratory results will also be graded using NCI-CTCAE v5.0, where possible. Parameters that have criteria available for both low and high values, i.e., hypo- and hyper-, will be summarized for both criteria. The same subject can be counted for both values if the subject has different laboratory values meeting each criterion. NCI-CTCAE grade of laboratory evaluations will be summarized by number and percentage of subjects for each visit. Shift tables of NCI-CTCAE grade change from baseline to worst post-baseline grade will also be presented.

Laboratory results based on central assessment will be used for summaries as described above. Laboratory results based on local assessment and bone marrow results will be listed only. The laboratory results may be displayed in figures.

7.5.2.1 Liver Enzymes and Total Bilirubin

The following potentially clinically significant criteria in liver function tests for Alkaline Phosphatase (ALP), Alanine Transaminase (ALT), total bilirubin, Aspartate Transaminase (AST) and their combination are defined. The subject's highest value during the study will be used.

Parameter	Criteria
ALT	> 3xULN > 5xULN > 8xULN
AST	> 3xULN > 5xULN > 8xULN
ALT or AST	> 3xULN
Total Bilirubin	> 2xULN
ALP	> 1.5xULN
ALT and/or AST AND Total Bilirubin(*)	(ALT and/or AST > 3xULN) and total bilirubin > 2xULN

(*) Combination of values measured within same sample

The number and percentage of subjects with potentially clinically significant values in liver enzymes and total bilirubin will be presented.

